6.7.1. Prohibited Prior and Concomitant Medications

Prohibited prior and concomitant medications are as follows:

- Any prior treatment with an approved or investigational agent for HBV.
- Treatments known to affect the immune system, such as corticosteroids (other than topical preparations), alkylating drugs, antimetabolites, cytotoxic drugs, radiation, immune-modulating biologics, allergy injections, immunoglobulins, interferons or other immunomodulating therapies are prohibited within 30 days of Screening and through the course of the trial.
- Live vaccines (such as live influenza vaccinations or live travel vaccinations) are also not permitted with 30 days of Screening and through the course of the trial.
- Receipt of any investigational drug or treatment within 30 days before Day 1 or planned use during the study period
- Change in any chronically administered medication or treatment within 30 days of Screening or inability to maintain these medications at the same dose through Day 169

In case of worsening or disease progression, study medication will be discontinued, and the above medications prohibited will be allowed, at the discretion of the investigator and Sponsor, if it is in the patient's best interest to initiate any treatment prohibited in the study.

Preventive COVID-19 vaccines that have regulatory approval or emergency use authorization will be allowed prior to IP dosing on Day 1, provided that their administration adheres to Exclusion Criterion 16. COVID-19 vaccination is also permitted during study participation. A \pm 3 day window is allowed for IP dosing if a COVID-19 vaccine is administered in proximity to a scheduled IP administration after Day 1. These vaccines will be captured as a concomitant medication.

6.8. Contraception

All female patients of childbearing potential must practice a highly effective method of birth control with low user dependency, as defined in Section 5.2, from Screening through one menstrual cycle after the last dose of study medication. Male patients with partners of childbearing potential must practice a highly effective method of contraception for 90 days after the last dose of study medication and refrain from sperm donation during this time.

6.9. Compliance

The injections will be administered by study personnel and therefore compliance with study medication dosing is not a concern. The study personnel will be appropriately trained on study medication administration procedures and documentation requirements prior to study start.

Non-compliance with study procedures will be reported to the Sponsor who will decide if persistent non-compliant patients should be withdrawn from continued study treatment.

7. PREMATURE DISCONTINUATION

7.1. Individual Patients

Patients can choose to discontinue study medication or participation in the study at any time, for any reason, without prejudice to their future medical care. Patients could be discontinued for any of the following reasons:

- Patient request/withdrawal of consent
- Noncompliance with study requirements
- Loss to follow-up
- Investigator discretion
- Sponsor request, including termination of the study by the Sponsor

In case of worsening or disease progression, study medication will be discontinued, and the medications prohibited in Section 6.7.1 will be allowed, at the discretion of the investigator and Sponsor, if it is in the patient's best interest to initiate any treatment prohibited in the study.

If a patient prematurely discontinues study medication before Day 169, Day 169/ET procedures will be performed. Patients who prematurely discontinue study medication will remain in the study for Follow-up Period study assessments, with the dates of visits adjusted to correspond to 13, 26, 39 and 52 weeks after the last dose of study medication.

Eligible patients who are randomized and withdrawn before their second dose of study medication will be replaced. Patients who have received two doses of study medication who are subsequently withdrawn from the study will not be replaced.

In consultation with the DMC, patients in the Sentinel Cohort may be replaced at any time to assure that the reliability and integrity of the data from this cohort remains intact.

7.1.1. Stopping Rules

In consultation with the DMC, the following Stopping Rules will be applied:

- ALT or AST $\geq 10 \times ULN$
- INR ≥ 1.3
- Total bilirubin $\geq 1.5 \times \text{ULN}$ (excluding patients with Gilbert Syndrome)
- Direct bilirubin $\geq 1.5 \times \text{ULN}$ (for patients with Gilbert Syndrome)
- SAEs
- Severe systemic reactogenicity event (see Appendix 1)

If any of the Stopping Rules are met in one or more patients in the sentinel cohort (ie, the first 12 patients dosed) and the event(s) is deemed possibly or probably related to study medication, dosing will be suspended pending DMC review. Similar procedures will be

applied if 2 or more patients in the sentinel or expanded study cohort together experience Stopping Rules deemed possibly or probably related to study medication at any time during the 24-week Treatment Period. DMC recommendations may include instituting modifications to ensure the safety of continued dosing or discontinuing the study.

If the study is halted based on a DMC decision or safety concern, the trial will only be restarted after notification of the competent authority via a substantial amendment.

7.1.2. Disease Progression / Need for Active Treatment

At the end of the clinical trial, either due to premature discontinuation or study completion, the decision about follow-on treatments and medical care will be made by the patient's physician or medical team in accordance with the usual standard of care. This will assure that patients have access to appropriate therapies in case of progression or other need for active treatment. Patients in need of active treatment will receive treatment based on the recommendations of American Association for the Study of Liver Disease [Terrault 2018], the Canadian Association for the Study of the Liver and Association of Medical Microbiology and Infectious Disease Canada [Coffin 2018], and European Association for the Study of the Liver guidelines [EASL 2017].

7.2. Study as a Whole

Both the Sponsor and the Investigator reserve the right to terminate the study at the Investigator's site at any time. Should this be necessary, the Sponsor or a specified designee will inform the appropriate regulatory authorities of the termination of the study and the reasons for its termination, and the Investigator will inform the IRB/IEC of the same. In terminating the study, the Sponsor and the Investigator will assure that adequate consideration is given to the protection of the patients' interests.

Possible reasons for termination are:

- Safety reasons the incidence of AEs in this or any other study using the same investigational product(s) indicates a potential health risk for the patients
- New scientific knowledge becomes known that makes the objectives of the study no longer feasible/valid
- Unsatisfactory enrollment of patients

8. DESCRIPTION OF STUDY PROCEDURES

See Section 4.6 for the Schedule of Events for the Screening and Treatment Periods (Table 1) and the Follow-up Period (Table 2).

8.1. Screening Assessments

8.1.1. Demographics

Demographic data and baseline characteristics will be recorded during Screening.

8.1.2. Medical History

A complete medical history will be obtained and recorded during Screening. Enquiries will be made regarding all body systems including allergies/drug sensitivities, past surgeries, substance abuse and any other diseases or disorders.

The medical history will include a history of hepatitis B flares, Fibroscan tests and measurements of qHBsAg, HBV DNA, and liver tests in the 24 months prior to Screening.

8.1.3. Fibroscan

A Fibroscan will be performed at Screening. The Fibroscan is not required if an examination was performed within 12 months before Screening, or if no fibrosis was seen on liver biopsy within 2 years before Screening.

8.1.4. Hepatitis B Genotyping

Hepatitis B genotyping will be performed at Screening if it has not been documented in the prior medical record.

8.2. Efficacy Assessments

8.2.1. Immunology

Whole blood samples will be collected and processed to isolate, cryopreserve and store PBMCs. This will be conducted at designated laboratory, which may include a central laboratory or laboratories at Investigator sites. Further details can be found in the laboratory manual.

Cryopreserved PBMC samples will be transferred to a designated laboratory for immunological analyses (IFN- γ ELISpot). The methods of ELISpot analysis will be detailed in the laboratory manual.

8.2.2. Virology

Blood samples will be collected for the assessment of virological parameters (qHBsAg, anti-HBsAg antibody, HBV DNA, HBV pg-RNA, HBcrAg, HBeAg, HBeAg antibody) at the times indicated in the Schedule of Events (Section 4.6). Isolation of serum or plasma

will be performed at the clinical site following methods detailed in the laboratory manual. Serum and plasma will be stored at the clinical site under appropriate conditions (as described in the laboratory manual) until shipment to a designated laboratory. The methods of virologic analysis will be detailed in the laboratory manual.

8.2.3. Stored Sample for Future Analyses

A single blood sample from patients will be collected for storage at the beginning of the study prior to dosing and at the end of the study, as indicated in Table 1. This sample will be used for future analyses not specified in the protocol. Analysis will be limited to HBV serologic and HBV-specific DNA and RNA; patients' DNA will not be analyzed.

8.3. Safety Assessments

8.3.1. Reactogenicity Assessments

Each patient will record local events, systemic events, and oral temperature in a diary daily for 7 days after each dose. Diaries will be distributed to patients at each dosing visit to record these events. Patients will also be provided thermometers for daily recording of temperatures and measuring devices for the recording the size of injection reactions. Events will be graded according to the FDA Guidance for Industry: Toxicity Grading Scale for Healthy Adult and Adolescent Volunteers Enrolled in Preventive Vaccine Clinical Trials [United States Food and Drug Administration 2007]. Unsolicited events reported by the patients outside of this 7-day reporting period will be recorded as AEs.

Microscopic hematuria will be assessed by urinalyses performed at the visits 7±2 days after Doses 1 and 2 of study medication, and after Doses 3, 4, 5, and 6 as per the Schedule of Events (Table 1).

Reactogenicity events will be categorized separately from AEs unless they are assessed as serious, in which case they will be reported as SAEs. A list of solicited reactogenicity events is provided in Appendix 1.

8.3.2. Adverse Events

Adverse events will be assessed by direct observation and patient assessments/interviews from Screening through the end of study. All AEs will be recorded through the end of the Treatment Period (Day 169 or ET). After that time, only MAEs, NCIs, and IMCs, which will be categorized as AEs, will be recorded through the end of the Follow-up Period (Day 505 or ET). A list of IMCs is provided in Appendix 2.

Details on the definitions, reporting, and management of AEs are provided in Section 9.

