ALT or AST ≥ 10×ULN, and Total and direct bili < 1.5×ULN, and INR < 1.3 ×ULN	Interrupt dosing Monitor liver panel weekly If ALT/AST fall to <5×ULN, restart dosing; if ALT/AST fall to <1.5×, stop weekly monitoring	If the event does not resolve in 4 weeks or recurs, consult medical monitor about discontinuing study medication
ALT or AST \geq 5×ULN, and Total or direct bili \geq 1.5×ULN, or INR \geq 1.3 ×ULN		Discontinue study medication
ALT or AST $< 5 \times ULN$, and Total or direct bili $\ge 1.5 \times ULN$, or INR $\ge 1.3 \times ULN$	Interrupt dosing Monitor liver panel weekly If total and direct bili fall to <1.5 ×ULN and/or INR falls to < 1.3× on 2 consecutive tests, stop weekly monitoring and restart dosing	If the event does not resolve in 4 weeks or recurs, consult medical monitor about discontinuing study medication

For patients with Gilbert Syndrome, the 1.5 × ULN criteria for total and direct bilirubin will be replaced with a 1.5 × ULN for direct bilirubin and there will be no monitoring criteria for total bilirubin [Fontana 2020]. Other etiologies of ALT, AST, total and direct bilirubin, and INR elevations, such liver injury induced by other drugs and other viral infections, should be ruled out and treated accordingly.

If a patient prematurely discontinues study medication on or before Day 169, the Day 169/Early termination procedures will be performed. Patients who prematurely discontinue study medication will remain in the study for follow-on study assessments.

Patients will be followed for 52 weeks after the last dose of study medication (504 days beyond Day 1 for patients who complete the 24-week Treatment Period). AEs and concomitant medications will be recorded from the signing of informed consent to Day 169, but only MAEs, NCIs, and IMCs, which will be categorized as AEs, will be followed subsequently. Likewise, concomitant medications will be recorded through Day 169, but only immunosuppressive medications, vaccines, and new HBV treatments or medications associated with MAEs, NCIs, SAEs, hepatitis flares, or hepatic injury will be recorded beyond this point. At the end of the clinical trial, the decision about follow-on treatments and medical care will be made by the patient's medical physician or medical team in accordance with the usual standard of care.

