- 1 If an authorized COVID-19 vaccine has been administered in proximity to a scheduled IP administration, a ± 3 day window is allowed for IP dosing.
- ^m After Day 169 or ET, only MAEs, NCIs and IMCs will be recorded.
- ⁿ A single blood sample will be collected for biobanking at the beginning of the study (prior to dosing on Day 1) and end of the study. This sample will be used for future analyses not specified in the protocol. Analysis will be limited to HBV serologic and HBV-specific DNA and RNA and patients' DNA will not be analyzed.
- ° Safety laboratory testing, including liver panel, for Doses 1 and 2 will be obtained during the visits conducted 7±2 days after these doses of study medication. Safety laboratory testing following Doses 3, 4 and 5 will be obtained in the interval from 7 days after dose administration and before the next dose of study medication is administered. Safety labs after Dose 6 will be assessed at the Day 169 visit.
- ^p Diaries will also be reviewed at the Day 85, Day 113, Day 141 and Day 169 visits

Table 2 Schedule of Events – Follow-up Period

	Follow-Up Period					
Study Visit	Day 232	Day 323	Day 414	Day 505 or ET ^a		
Completion of Week (number)	33	46	59	72		
Window (days)	±10 days	±10 days	±10 days	±10 days		
Visit may be conducted at home or work or in part as a telemedicine visit ^b	X		X			
Immunosuppressive medications, vaccines, and new HBV treatments (only) ^c	X	X	X	X		
Targeted and symptom-driven PE	X	X	X	X		
Height and weight				X		
Vital signs ^d	X	X	X	X		
ECG ^d				X		
Hematology and serum chemistry	X	X	X	X		
Liver panel	X	X	X	X		
HBV serology and viral markers ^e		X		X		
Whole blood for PBMC isolation		X		X		
MAEs, NCIs and IMCs (only) ^f	X	X	X	X		

AE = adverse event; ECG = electrocardiogram; ET = early termination; HBV = hepatitis B virus; HIV = human immunodeficiency virus; MAE = medically-attended adverse event; NCI = new-onset chronic illness; IMC = immune-mediated medical condition; PBMC = peripheral blood nonnuclear cell; PE = physical examination.

^a If a patient prematurely discontinues study medication before Day 505, Day 505/Early termination procedures will be performed.

^b A telemedicine visit would include a home visit by appropriate trained personnel to perform a target and symptom-driven physical and obtain vital signs and safety laboratories. The remaining portions of the visit may be conducted virtually by the study investigator.

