9.1.4. Medically Attended Adverse Event

An MAE is an AE resulting in hospitalization, emergency room visit, or visit to or from medical personnel (other than routine health care visits).

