9.2. Reporting Responsibilities and Periods

It is the responsibility of the Investigator or Subinvestigator(s) to perform periodic assessment of AEs. AEs spontaneously reported by the patient or reported in response to an open question from the study personnel (eg, 'Have you had any health problems since the previous visit/you were last asked?') or revealed by observation will be recorded.

AEs and concomitant medications will be recorded from the signing of informed consent to Day 169, but only MAEs, NCIs, and IMCs, which will be categorized as AEs, will be followed subsequently through Day 505. Concomitant medication collection will align with AE collection. The AE term, date of AE onset, date of AE resolution (if applicable), severity, causality, action taken for the AE, outcome and whether or not the AE is an MAE, NCI, and or SAE will be recorded.

AEs must be monitored until they are resolved or stabilized, are clearly determined to be due to a patient's stable or chronic condition or intercurrent illness(es), or follow-up is no longer possible. Data describing AEs will be recorded in the patient's medical record and as appropriate, an SAE report form. SAEs will be reported to the Sponsor as described in Section 9.7.

Any SAE that the Investigator considers to be possibly or probably related to study medication and occurs at any time after completion of the study must be reported to the Sponsor or designee. If at the time the Investigator initially reports an SAE, the event has not resolved, the Investigator must provide a follow-up report as soon as it resolves (or upon receipt of significant information if the event is still ongoing).

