9.7.2. Reporting of Serious Adverse Events

Serious AEs require reporting to the Sponsor or designee within 24 hours, regardless of the relationship of the event to the study treatment regimen. Refer to Section 9.1.7 for the definition of an SAE. Procedures for recording and reporting SAEs will be detailed in a separate Safety Management Plan for processing SAEs, expedited safety reports, and the emergency unblinding of patients.

Within 24 hours of the Investigator's observation or learning of an SAE, the Investigator should notify Pivotal, S.L.U. (Pivotal Pharmacovigilance) by completing the SAE forms as thoroughly as possible with all available details of the event, including a determination of causality (even if preliminary), and signing them. The Investigator should communicate with Pivotal Pharmacovigilance if input is needed to complete the SAE assessment. Investigator causality determination and signature MUST be included for all SAEs. The completed SAE form and cover sheet should be sent by email or fax to Pivotal Pharmacovigilance.

Pivotal Pharmacovigilance

North America: (Fax) [contact]

(Phone) [contact]

Europe/UK/Asia-Pacific: (Fax) [contact]

(Phone) [contact]

e-mail: [contact]

If not all information regarding an SAE is initially available, the Investigator should not wait to receive additional information before completing the AE eCRF and SAE forms. For initial SAE reports, the Investigator should record all case details that can be garnered on the SAE form and the AE eCRF page. Relevant follow-up information is to be submitted on updated SAE forms as soon as it becomes available.

If there are questions regarding reporting an SAE or if information needs to be transmitted that cannot be recorded on the SAE forms (e.g., discharge summaries, laboratory reports), the Investigator should contact Pivotal Pharmacovigilance.

For unexpected serious adverse drug reactions (SUSARs), blinded reports will be disseminated and provided to Investigators at each study site.

When required and according to local law and regulations, unblinded SUSARs or other SAEs will be reported by an unblinded designee to the IRB/EC and regulatory authorities.

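### The post-Day-169 recording lists leave out serious adverse events, which contradicts the protocol's own SAE rules, and the SAP's supplementary follow-up tables repeat the omission

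*Protocol*

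**What the plan says.** All adverse events are recorded up to Day 169 or early termination (ET). For the time after that, protocol 8.3.2 states: "After that time, only MAEs, NCIs, and IMCs, which will be categorized as AEs, will be recorded through the end of the Follow-up Period". Section 9.2 says "only MAEs, NCIs, and IMCs, which will be categorized as AEs, will be followed subsequently through Day 505", and section 4.1 and the Study Summary carry the same restriction. Footnote m of Table 1 and footnote f of Table 2 read "After Day 169 or ET, only MAEs, NCIs and IMCs will be recorded", and the Table 2 row for these events is marked as covering them alone. SAP 2.3 repeats the list. SAEs are in none of these places.

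Other sections set a different rule:

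- Section 9.7.2: "Serious AEs require reporting to the Sponsor or designee within 24 hours, regardless of the relationship of the event to the study treatment regimen". For initial reports it adds that "the Investigator should record all case details that can be garnered on the SAE form and the AE eCRF page". Neither sentence has an end date.
- Section 9.7.3 requires the event that led to a death to be entered on the same two forms, again with no end date.
- Section 4.1, on concomitant medication after Day 169: "medications associated with MAEs, NCIs, SAEs, hepatitis flares, or hepatic injury will be recorded beyond this point". Section 9.2 says that medication collection is to match AE collection.
- Section 9.2 also has a reporting duty for "Any SAE that the Investigator considers to be possibly or probably related to study medication and occurs at any time after completion of the study".

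On outputs, the SAP addendum names three follow-up tables to supplement those of the Week 24 analysis: 14.3.3.1.2 (MAEs), 14.3.3.2.2 (NCIs) and 14.3.3.3.2 (IMCs). It also names a set of listings, which includes the SAE listing 16.2.7.2.

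**The concern.** The schedule tables and their footnotes are what site staff work from at a visit. They tell staff to record three categories and nothing else, while the SAE section tells them to enter SAEs on the AE page whenever they occur. An event that is serious but falls in none of the three categories is then subject to two opposite instructions. If a site follows the schedule, the event may reach neither the clinical database nor any output by arm. If it is sent to pharmacovigilance only, the two databases disagree.

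Safety is a secondary objective, and protocol 3.4 asks for safety endpoints to be assessed separately for the 52-week Follow-Up Period. With about 40 patients per arm, a single death or other serious event would matter to the safety account.

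**Working it through.** **1. Length of the interval.** Inputs: last dose on Day 141 (protocol 6.3), end of treatment on Day 169 ±2 days (Table 1), final visit on Day 505 ±10 days (Table 2).

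- The plan's own figures reproduce: (505 − 141)/7 = 364/7 = 52.0 weeks after the last dose, and 505 − 1 = 504 days beyond Day 1.
- Restricted recording: 505 − 169 = 336 days, and 336/7 = 48.0 weeks.
- With the visit windows, the shortest is (505 − 10) − (169 + 2) = 324 days (46.3 weeks) and the longest is (505 + 10) − (169 − 2) = 348 days (49.7 weeks).
- For a patient who stops early, the restriction starts at ET, so the interval can differ from 48 weeks.

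**2. The two rules side by side.**

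- Sections 4.1, 8.3.2 and 9.2, the Table 1 and 2 footnotes and SAP 2.3: three categories only, to the end of follow-up. SAEs are not named.
- Sections 9.7.2 and 9.7.3: SAEs whatever their relationship to treatment, and the event behind any death, on the SAE form and the AE eCRF page. No cut-off.
- Medication rule: treatments given for SAEs are recorded after Day 169, which makes sense only if the SAEs are recorded too. If medication collection is to match AE collection, as 9.2 says, the AE list is one item short.

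**3. Which SAEs fall between the rules.** Section 9.1.4 defines the broadest category: "An MAE is an AE resulting in hospitalization, emergency room visit, or visit to or from medical personnel", with routine visits excepted. Set against the seriousness criteria in 9.1.7:

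- Hospitalization is always an MAE.
- Life-threatening events, lasting incapacity and other important medical events will nearly always involve an emergency room or a non-routine medical visit, and so be MAEs. Even the 9.1.7 example of bronchospasm treated intensively at home would ordinarily bring medical personnel to the patient.
- A death with no medical contact need not be an MAE. Nor need it be an NCI (a new chronic diagnosis) or an IMC (listed in Appendix 2 or judged immune-mediated).
- Section 9.6 has any overdose documented as an SAE. One that leads to no medical visit need be none of the three.

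The affected set is therefore small but not empty. The documents give no rate from which to estimate how many such events to expect.

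**4. The outputs.** The addendum's three supplementary tables mirror the restricted list. The table of serious treatment-emergent events, 14.3.2.1, is not among the outputs to be generated after Week 24, and it is not split by period. An SAE arising in follow-up after the Week 24 lock would thus be shown as an SAE only in listing 16.2.7.2, with no count by arm. The statement closing safety follow-up (SAP section 2 and addendum) rests on there being no ongoing MAEs, NCIs or IMCs, and does not mention SAEs.

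**The case against.** A reader might infer that SAEs outside the three categories simply go unrecorded for 48 weeks. The documents do not support that. Sections 9.7.2 and 9.7.3 require an eCRF entry with no time limit, and 9.7.3 covers the clearest example, death. Section 8.3.2 itself refers to section 9 for reporting. The medication rule presupposes that SAEs are captured in follow-up, as does the reporting of pregnancies, with their complications, through Day 505 (9.7.4). The duty to report related SAEs after study completion reads naturally as an extension of full reporting during the study. Sections 4.1 and 9.2 also speak of events being followed, which is looser than recorded.

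Nor is 336 days the size of a gap: hospitalized and otherwise medically attended SAEs are recorded as MAEs throughout it.

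On outputs, listing 16.2.7.2 is kept in the addendum, and the SAP's Appendix 1 marks 14.3.2.1 for the final report without a Day 169 limit. Finally, the study has been terminated, so rewording the protocol can no longer change data collection.

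All of this limits the point, but the contradiction remains. Section 8.3.2 and both schedule footnotes do say that only the three categories are recorded, and no text says which rule prevails. The addendum names the tables to be added after Week 24, and none of them is an SAE table.

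**Conclusion.** The plan contradicts itself on whether SAEs are recorded after Day 169, and the supplementary outputs follow the narrower rule. The consequence is a risk of omission, not an established loss of data: a site following the schedule could leave an SAE without medical contact off the eCRF during about 48 weeks (46.3 to 49.7 weeks with the visit windows, for patients who complete treatment). Few events are likely to be affected, because most SAEs are also MAEs, and the number cannot be estimated from the documents.

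The output part stands however the protocol is read: even a correctly recorded SAE arising after the Week 24 lock has no SAE table by arm in the addendum. This rests on taking the addendum's list as the complete set of tables produced after Week 24. If 14.3.2.1 is rerun on the final data, the event would be counted there, though still not separately for the Follow-Up Period.

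**What to change.** - Reconcile the recording lists with 9.7.2 and 9.7.3 by adding *SAEs (including deaths)* to each post-Day-169 list: the protocol Study Summary, 4.1, 8.3.2, 9.2, Table 1 footnote m, Table 2 (row and footnote f), and SAP 2.3.
- Add a Follow-Up Period SAE table by arm beside 14.3.3.1.2, 14.3.3.2.2 and 14.3.3.3.2.
- Because the study has been terminated, state in the SAP that SAEs, as well as MAEs, NCIs and IMCs, were checked when safety follow-up was closed. Comparing the SAE forms received with the AE eCRF pages for that period would support the statement.

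The cost is wording and one table. Section 9.7.2 already obliges sites to report SAEs, and 9.2 has each AE flagged for seriousness, so no new procedure or data item is needed. For this study the useful parts now are the table and the closing statement. The protocol wording serves consistency, and any later study that reuses the text.
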